6.1.6 Early Termination Visit

If the subject withdraws from the study after the Baseline visit and before completion of all study visits, they will be invited to participate in an Early Termination Visit within 7 days of stopping treatment.

The following procedures will be performed virtually via Zoom videoconferencing no more than 4 days before the in-person office visit:

- Administer cognitive assessments
- Administer functional and mood assessments
- Assess technology and study supplement compliance.
- Review and document concomitant medications, supplements, and therapies
- Assess and document AEs and changes to medical history

The following procedures will be performed at the in-person office visit:

- Measure Vital Signs
- Blood draw for safety labs and biomarker analysis
- Assess study supplement compliance

6.1.7 Protocol Deviations

A protocol deviation is any noncompliance with the current clinical trial protocol. The noncompliance may be on the part of the subject, the PI, or the study staff. As a result of deviations, corrective actions will be developed by the PI and implemented promptly. All deviations from the protocol must be addressed in the subject's documents. Protocol deviations will be sent to the IRB per their guidelines and entered in the Protocol Deviations Log in the EDC System.

6.1.8 Missed Visits and Procedures

Missed visits and any procedures not performed (not attempted) for reasons other than illness or injury will be reported as a protocol deviation. Procedures or visits not performed due to illness, injury, or disability, including procedures that were attempted but failed (i.e. weight unable to be obtained due to subject immobility) will not be reported as protocol deviations.

7 CLINICAL ASSESSMENTS AND OUTCOME MEASURES

7.1 Clinical Variables

Assessments will be performed at designated time-points throughout the study for clinical evaluation. In addition to the assessments evaluated below, subjects will provide information on their demographics, past medical and AD history, family history, and concomitant medication usage.

A Crossover, Randomized Block Sequence, Double-Blind, Placebo-Controlled Trial for Nicotinamide Riboside in Subjective Cognitive Decline and Mild Cognitive Impairment in Aging

Version:4.4

7.1.1 Safety Measures

7.1.1.1 Vital Signs, Height, Weight

Vital signs, including systolic and diastolic blood pressure, pulse rate (radial artery)/minute, respiratory rate/minute, and temperature will be assessed at specified visits. Verbal weight may be documented for those subjects utilizing a wheelchair. Height and weight will be measured and recorded at the Lead-In only.

7.1.1.2 Clinical Laboratory Assessments

Study participants will be asked to provide approximately 13 mL of blood for safety lab analysis at the Lead-In visit (with an additional draw at the Follow-Up visit if any Day 140 labs are abnormal and clinically significant), for a total of 22 ml (about 1.5 tablespoons) throughout the study. The participant will have his or her whole blood collected by either a nurse or phlebotomist from a peripheral vein. Blood will be handled, processed, and analyzed in accordance with regulations set forth by the American Society for Clinical Pathology and the College of American Pathologists.

Tests for Complete Blood Count (CBC) and Prothrombin Time and International Normalized Ratio (PT/INR) which are required prior to performing a lumbar puncture may be performed using CLIA waived point of care testing using the Sysmex XW-100 CBC analyzer and the Roche CoaguChek XS Plus PT/INR analyzer. This will involve an additional fingerstick blood draw.

The investigator may order additional testing, if thought to be necessary, to further assess an adverse event (AE).

7.1.1.3 Physical and Neurological Examination

A physical and neurological examination will be performed at Lead-In, Baseline (Day 28), Crossover (Day 84), and End of Study (Day 140). The following systems will be examined: general appearance, head, eyes, ears, nose, throat, neck, chest, heart, abdomen, extremities, edema, peripheral vascular, skin and appendages, musculoskeletal, central nervous system and back.

7.1.1.4 Adverse Events

Once the informed consent form has been signed by the subject, inquiry about all adverse events (AEs) will be performed at each study visit.

7.1.2 Clinical Assessments

7.1.2.1 Neuropsychiatric and Functional Assessments

All neuropsychiatric questionnaires will be administered via Zoom videoconference; any required materials will be mailed or given to subjects prior to the visit.

A Crossover, Randomized Block Sequence, Double-Blind, Placebo-Controlled Trial for Nicotinamide Riboside in Subjective Cognitive Decline and Mild Cognitive Impairment in Aging

Version:4.4

7.1.2.1.1 Beck Anxiety Inventory (BAI)

The Beck Anxiety Inventory²¹ (BAI) is a 21-item, self-administered questionnaire that measures the presence and severity of anxiety in psychiatric populations. It was constructed to avoid confounds due to comorbidity of depression, and it has been found to be highly valid, reliable, and consistent²³. The BAI lists 21 common symptoms of anxiety and asks the subject to rate the severity with which they experience each symptom (not at all, mildly, moderately, or severely). Scores of 0-21, 21-35, or 36-63 indicate low, moderate, or severe anxiety, respectively.

7.1.2.1.2 Beck Depression Inventory (BDI)

The Beck Depression Inventory²² (BDI) is a widely used assessment of depression severity used in clinical and research settings. It is a 21-item, self-administered rating inventory with a mean internal consistency of 0.86^{24} . The BDI ranks responses to several domains of depression, including mood changes, guilt, self-image, suicidality, affect, and apathy on a scale from 0 to 3 and provides an assessment of the level of depression, spanning minimal to mild to moderate to severe depression.

7.1.2.1.3 Memory Function Questionnaire (MFQ)

The Memory Function Questionnaire²⁰ (MFQ) is an 8 question, self-administered functional assessment which measures the frequency and severity of self-perceived memory-related capabilities. The questionnaire involves a general rating of frequency of memory problems, a retrospective intraindividual comparison of memory decline, an assessment of forgetting frequency, an assessment of forgetting severity, and an assessment of self-derived mnemonic device usage. The MFQ was determined to show high internal consisteny²⁰ and moderate concurrent validity with subsequent performance on clinical measures of memory²⁵.

7.1.2.1.4 Behavior Rating Inventory of Executive Function (BRIEF-A)

The Behavior Rating Inventory of Executive Functioning¹⁹ (BRIEF-A) is a standardized rating scale to assess self-regulation and executive function in everyday behaviors. It is a 75-item scale including a Behavioral Regulation Index consisting of inhibition, shifting, emotional control, and self-monitoring scales and a Metacognition Index consisting of initiation, working memory, planning/organization, task monitoring, and organization of material scales. This study will only use the BRIEF-A self and not the informant report.

7.1.2.1.5 Lawton Instrumental Activities of Daily Living (IADL) Scale

The Lawton Instrumental Activities of Daily Living Scale (IADL) Scale²⁶ covers 8 domains of functioning and was designed to assess independent living skills in older adults²⁷. IADLs are more complex than basic Activities of Daily Living (ADLs) and are therefore more sensitive to disruption due to cognitive impairment. This scale takes about 10 minutes to complete and is administered by a trained rater who will determine whether participants are functionally impaired and therefore not eligible to participate in the study per inclusion criteria 2.

7.1.2.2 Neurocognitive Assessments

All neurocognitive assessments will be administered via Zoom videoconference.

A Crossover, Randomized Block Sequence, Double-Blind, Placebo-Controlled Trial for Nicotinamide Riboside in Subjective Cognitive Decline and Mild Cognitive Impairment in Aging

Version:4.4

7.1.2.2.1 Montreal Cognitive Assessment (MoCA)

The Montreal Cognitive Assessment (MoCA)²⁸ is a commonly used screening tool in clinical trials and research settings to measure potential presence of cognitive impairment. The MoCA measures five areas of cognitive function: orientation, visuospatial, attention and calculation, recall, and language. This measure will be completed as part of screening procedures carried out by the Northern Light Healthcare site and should take approximately 10 minutes.

7.1.2.2.2 Telephone Montreal Cognitive Assessment (T-MoCA; also referred to as MoCA-Blind)

The Telephone Montreal Cognitive Assessment²⁸ (T-MoCA) is a commonly utilized abbreviated cognitive screener adapted from the full Montreal Cognitive Assessment for the purposes of measuring levels of cognitive impairment over the telephone. The telephone MoCA measures five areas of cognitive function: orientation, abstraction, attention and calculation, memory, and language. The telephone MoCA will take approximately 10 minutes to complete and will be administered by experienced raters following the administration recommendations specified by the test publishers. The telephone MoCA will be administered only at the Screening visit to determine subject eligibility, and will require participants to achieve a telephone MoCA score of 16-22 inclusive.

7.1.2.2.3 Repeatable Battery for the Assessment of Neuropsychological Status (RBANS)

The Repeatable Battery for the Assessment of Neuropsychological Status¹⁵ (RBANS) is a commonly used 25-minute, standardized neurocognitive battery assessing functioning across multiple cognitive domains. It is designed to be administered repeatably, with several equivalent alternate forms available. The RBANS measures a total of five neurocognitive domains using twelve subtests: immediate memory (List Learning and Story Memory), visuospatial/constructional (Figure Copy and Line Orientation), language (Picture naming and Semantic Fluency), attention (Digit Span and Coding), and delayed memory (List Recall, List Recognition, Story Memory, and Figure Recall). The RBANS has been shown to be effective at both detecting and characterizing forms of dementia. The Delayed Memory domain has been shown to be particularly sensitive to discriminating MCI due to Alzheimer's disease from controls, and also is predictive of cerebral amyloid burden¹⁵. The RBANS will be administered at Baseline, Crossover, and End of Study using alternate forms. The RBANS will be administered virtually via Zoom videoconference. The coding subtest response form will be mailed or given to subjects before their scheduled visits along with a prepaid envelope for the form to be returned.

7.1.2.2.4 Millisecond Continuous Performance Test (CPT)

The Continuous Performance Test is a test of sustained attention and alertness in which subjects are presented with a string of letters²⁹. The subject is instructed to press a button every time they see an X and not to press it for any other letter. Letters are presented for five minutes. The subject is then given a brief break before continuing to the next part of the study, the AX task. In this section, the subject is told to press the button when they see an X that follow right after an A but not when there is an X that is not preceded by an A. The subject is then presented with another five-minute block of letters. This section of the task is also a test of inhibition and executive control. Task administration will utilize Millisecond Inquisit software, a computerized stimulus presentation platform optimized for temporally precise stimuli presentation and reaction time recording of psychological assessments. The CPT will be administered at Baseline (Day 28), Crossover (Day 84), and at End

A Crossover, Randomized Block Sequence, Double-Blind, Placebo-Controlled Trial for Nicotinamide Riboside in Subjective Cognitive Decline and Mild Cognitive Impairment in Aging

Version:4.4

of Study (Day 140). Task administration will utilize Millisecond Inquisit Lab software, a stimulus presentation platform optimized for temporally precise stimuli presentation and reaction time recording of digitized psychological assessments. Inquisit Web requires only a subject code and no personally identifiable information.

7.1.2.2.5 Test of Premorbid Functioning

The Test of Premorbid Functioning³⁰ (TOPF) provides an estimate of premorbid intellectual functioning that allows for comparisons with an individual's current cognitive status. The test consists of a list of 70 words that have atypical grapheme to morpheme translations. A premorbid estimate of intelligence is calculated based on the raw TOPF score (number of words correctly read) and up to 13 demographic variables. The tests demonstrates excellent reliability across the age groups included in this study (Ages 60-90 = 0.98-0.99), in MCI (0.98), and in AD $(0.99)^{31}$.

7.1.2.2.6 Trail Making Test

The Trail-Making Test¹⁶ (TMT) is a graphomotor letter and number-letter sequencing task that will be administered to test processing speed, mental flexibility, and set-switching. The test takes approximately 5 minutes to complete. The standard, paper version of this test cannot be administered virtually, so the oral Trail Making Test (45) will be used at all study visits.

7.1.2.2.7 Brief Visuospatial Memory Test-Revised (BVMT-R)

The Brief Visuospatial Memory Test-Revised¹⁸ (BVMT-R) is a test of visuospatial learning and memory with six equivalent alternate forms.²³ The BVMT-R has three learning trials, a 25-minute delay, and then delayed recall and recognition trials. The visual stimuli for each learning trial will be presented digitally. The recall and recognition portion of this assessment will be given in the traditional, pencil and paper format and scored according to published administration instructions and norms. Permission to adapt BVMT-R stimuli into a digital format was granted by the publisher of the test. The BVMT-R will be administered at Baseline, Crossover visit, and at End of Study.

7.1.2.4 Phlebotomy for AD Biomarkers

Subjects will provide additional blood samples for AD biomarker analysis at Lead-In and each block visit (Day 28-up to and including Day 140). Biomarker analysis will include NfL, A β 42, A β 40, tau, GFAP, neurogranin, and other analyses. At each block visit (Days 0-140), 30 ml (2.0 tablespoons) of blood will be collected for research analyses, for a total of approximately 120 ml (8 tablespoons) over the course of the study.

7.1.2.5 Magnetic Resonance Imaging (MRI)

Subjects will be given the opportunity to participate in an optional MRI sub-study at Baseline (Day 28), Crossover (Day 84), and/or End of Study (Day 140). Subjects electing to participate will be asked to complete all 3 MRIs to be part of the sub-study. Data will be collected on a 3-Tesla Siemens scanner with the following scan sequences: a high resolution T1-weighted scan, T2 FLAIR, resting state BOLD MRI, and pCASL at rest.

Resting state BOLD measures low-frequency spontaneous fluctuations in BOLD signal across time, where correlations of this spontaneous activity between brain regions are thought to reflect functional

A Crossover, Randomized Block Sequence, Double-Blind, Placebo-Controlled Trial for Nicotinamide Riboside in Subjective Cognitive Decline and Mild Cognitive Impairment in Aging

Version:4.4

connectivity. The 10-minute rsfMRI scan will be acquired with whole-brain echo planar imaging (EPI) time series with a voxel size of 2x2x2 mm isotropic, TR/TE = 4000/30 ms, acquisition matrix = 64x64, and 40 axial slices. Subjects will be instructed to keep their eyes open throughout the duration of the scan. rsfMRI data will be processed within the FreeSurfer FS-FAST stream using standard pre-processing steps including motion correction, masking of non-brain tissue, registration to the anatomical high-res image, sampling to the surface, and surface smoothing by 5 mm. Temporal filtering to extract signals in the 0.008-0.08 Hz frequency band will be performed, followed by linear regression to factor out mean global signal, average signal from white matter, and average signal from ventricular CSF regions. To perform functional connectivity analyses, we will use a seed-based approach to examine temporal correlations between the mean time course within anatomically-defined nodes and the rest of the brain.

ASL-MRI is another indicator of brain function, quantifying regional cerebral blood flow, which in turn is linearly coupled to regional brain metabolism and neuronal activity^{36,37}. It is especially well suited to drug trials in which change from baseline is of prime interest^{38–40}. Pseudo-Continuous ASL (pCASL)⁴⁰, which provides excellent sensitivity and temporal stability⁴¹ and accurately differentiates AD from other causes of dementia⁴², will be used in the protocol. The single shot pCASL scan will be acquired with the following parameters: 24 cm field of view, 2x2x2 mm isotropic, TR/TE = 4300/3.2 ms, acquisition matrix = 64x64, slice thickness = 6mm, temporal bolus = 1800 ms with a 1800 ms post labeling delay. Corresponding field map scans will also be acquired to correct for blurring and signal dropout during image processing. All data processing and analysis will utilize tools available through FSL's Bayesian Inference for Arterial Spin Labeling MRI (BASIL) toolbox.

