3.2 Study Objectives

A Crossover, Randomized Block Sequence, Double-Blind, Placebo-Controlled Trial for Nicotinamide Riboside in Subjective Cognitive Decline and Mild Cognitive Impairment in Aging

Version:4.4

The primary objective of the study will be:

1. To measure the effect of NR vs PBO on RBANS.

The secondary clinical objectives of the study will be:

- 1. To measure the effect of NR vs PBO on other, standard assessments of cognition, functional activities, and neuropsychiatric symptoms.
- 2. To measure the effect of NR vs PBO on daily assessments of cognition, functional activities, and neuropsychiatric symptoms.
- 3. To monitor the safety and tolerability of NR in volunteers with SCD or MCI.

The exploratory biomarker objectives of the study will be:

- 1. To measure the effect of NR on plasma biomarkers of metabolic target engagement and central nervous system (CNS) neural and glial integrity measurable in blood.
- 2. To measure the effects of NR on cerebral neurophysiology (in an optional sub-study) using resting state functional magnetic resonance imaging (rs-fMRI). Connectivity will be measured with rsBOLD and regional cerebral blood flow will be measured with pseudo-continuous arterial spin labeling (pCASL).
- 3. To measure the effect of NR on cerebrospinal fluid (CSF) biomarkers (in an optional sub-study) of metabolic target engagement and emerging biomarkers of relevance to AD/ADRD.

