4.2 Recruitment

Approximately 60 subjects will be screened, and after screening, approximately 40 subjects are expected to complete the study. All subjects will be given the option to participate in the optional repeat LP sub-study and the optional MRI sub-study until 12 subjects have completed each sub-study. Subjects will be given the choice to complete either the repeat LP sub-study, the MRI sub-study, or both.

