When conducting study analyses we can also calculate 95% confidence intervals for the difference in response for active treatment versus placebo treatment for descriptive purposes. Similar analyses will be applied to all

A Crossover, Randomized Block Sequence, Double-Blind, Placebo-Controlled Trial for Nicotinamide Riboside in Subjective Cognitive Decline and Mild Cognitive Impairment in Aging

Version:4.4

outcomes. All outcomes in this pilot study are considered exploratory and no claims are attached to them, thus multiple comparison correction is not applied. Therefore P value <0.05 will be considered significant.

Carryover is always a potential confound in crossover studies. While the pharmacokinetic half-life of NR is short (2.7 hours), its pharmacodynamic effects may be long-lived and we cannot exclude carryover and practice effects affecting measures in successive assessments if NR precedes PBO. We do not expect carryover pharmacological effects from PBO, but assessment practice effects might differentially affect measurements made in an NR intervention period that follows PBO. This may be difficult to gauge with our primary RBANS outcome measure taken only once at the beginning/end of each intervention period. However, we will have other resources with which to evaluate this using our exploratory outcomes, especially the daily cognition measures. We will investigate various adjustments for carryover, such as discarding the first measurements in an intervention period on outcomes measured daily, to determine whether results are sensitive to carryover. These adjustments can allow for potential differential carryover by intervention regimen.

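### Section 9.1's rule of no multiplicity correction with P<0.05 makes no exception for brain-wide connectivity maps; tested location by location, these would almost always show falsely significant regions

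*Combined protocol and SAP*

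**What the plan says.** Section 3.2 makes the imaging question a treatment question. Exploratory biomarker objective 2 is "To measure the effects of NR on cerebral neurophysiology (in an optional sub-study) using resting state functional magnetic resonance imaging". Section 4.2 offers the optional MRI sub-study "until 12 subjects have completed each sub-study".

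For the connectivity analysis, Section 7.1.2.5 plans a "seed-based approach to examine temporal correlations between the mean time course within anatomically-defined nodes and the rest of the brain". Nodes is plural, but the seeds are not listed. The steps described around this sentence (motion correction, masking, registration, surface sampling, 5 mm smoothing, filtering, nuisance regression) all prepare the data. None is a rule for declaring an NR effect, and no voxel, vertex or cluster threshold is given. Section 3.2.1 mentions the default mode network but does not declare it as the measure to be tested.

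Section 9.1 sets out a paired t-test and a mixed model for the RBANS Total Scale score and then says "Similar analyses will be applied to all" outcomes. On multiplicity it says "All outcomes in this pilot study are considered exploratory and no claims are attached to them, thus multiple comparison correction is not applied". The next sentence is "Therefore P value <0.05 will be considered significant". No section makes an exception for imaging.

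**The concern.** Leaving out a correction across a short list of named scales is defensible in a pilot, because readers can count the tests and discount accordingly. A connectivity map is different: one outcome holds a large and usually unreported number of tests. Applied to a map, the Section 9.1 rule declares about one location in twenty significant when NR has no effect.

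At stake is the interpretation of exploratory objective 2. Participants in the sub-study are asked to undergo three MRI scans each. If the result is a list of regions with P<0.05, the existence of that list says little, because such a list is expected without any effect.

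**Working it through.** The documents give no number of tests, no family-wise error rate and no power figure for imaging, so there is no stated figure to reproduce. The only stated error figure is the 0.05 threshold.

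**Inputs**
- Per-test threshold 0.05 (Section 9.1). Sidedness is not stated; two-sided is assumed and does not change the error rate.
- Search space: each seed against the rest of the brain (Section 7.1.2.5).
- Completers: 12 (Section 4.2).
- Effective number of independent tests per seed map, m: not in the documents. Assumed, and varied.

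**Step 1. False positives when NR has no effect.** The chance of at least one is 1 − (1 − 0.05)^m; the expected number is 0.05 × m.

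| m | Chance of at least one | Expected number |
|---|---|---|
| 10 | 1 − 0.95^10 = 40.1% | 0.5 |
| 20 | 64.2% | 1 |
| 50 | 92.3% | 2.5 |
| 90 | 99.0% | 4.5 |
| 100 | 99.4% | 5 |
| 500 | about 100% | 25 |
| 1,000 | about 100% | 50 |

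This is per seed. Further seeds add to it.

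**Step 2. Does smoothing rescue the rule?** Neighbouring locations are correlated, so the independence formula was checked by simulation: 300 null datasets per setting, 12 subjects, a paired t-test of NR minus placebo at every point (two-sided 0.05), on Gaussian-smoothed two-dimensional fields of 2 mm pixels. Field size and smoothing width (full width at half maximum, FWHM) are assumptions; the first row uses the protocol's 5 mm.

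| Field | FWHM | Datasets with a false positive | Mean number of clusters |
|---|---|---|---|
| 128 × 128 mm | 5 mm | 100% | 69 (minimum 47) |
| 128 × 128 mm | 10 mm | 100% | 21 |
| 128 × 128 mm | 20 mm | 99.7% | 5.8 |
| 64 × 64 mm | 20 mm | 91.3% | 1.8 |

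Between 4.8% and 5.1% of the map was falsely positive in every setting. Smoothing merges false positives into fewer clusters but does not remove them.

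**Step 3. With map-level control.** Bonferroni serves as the simplest example. At m=100 the per-test level is 0.05/100 = 0.0005, and 1 − (1 − 0.0005)^100 = 4.9%. At m=10,000 the result is again 4.9%. A single pre-specified connection gives 5.0%.

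**Step 4. Why control must span the seeds.** If each of five seed maps were controlled separately at 5% (five is illustrative, maps taken as independent), the chance of a false finding somewhere would be 1 − 0.95^5 = 22.6%.

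**The case against.** **The outcomes are exploratory and carry no claims.** The plan says so for every outcome, and that limits the weight put on any imaging result. It does not change the error rate, and the next sentence of Section 9.1 still attaches the word significant to P<0.05.

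**A location-by-location NR–placebo test is not written down.** This is the strongest objection, and part of it stands. Section 7.1.2.5 describes how connectivity is derived from a scan. Section 9.1's methods are written for scalar scores, and its no-correction sentence may have been meant for multiplicity across endpoints. Section 3.2.1 speaks of connectivity strength within networks, which would fit a few network-level values. A reader might infer that the plan commits itself to an uncorrected whole-brain map; the documents do not go that far. But correlating several seeds with the rest of the brain most naturally yields maps, Section 9.1 extends its rule to all outcomes, and nothing restricts the analysis to a few connections. Even ten connections would give 40.1%.

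**The imaging analysts would correct in any case.** If so, the plan should say so. As it stands, the general rule points the other way and the threshold could be chosen after the maps are seen.

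**The number of tests is unknown.** This is right. A reader might take it from the acquisition settings, "acquisition matrix = 64x64, and 40 axial slices": 64 × 64 × 40 = 163,840 voxels, and 5% of that is 8,192. The documents do not support this as a count of tests, because masking and surface sampling remove many of those voxels before any analysis. The assumed range of m is the proper basis.

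**Conclusion.** The concern holds conditionally. If NR–placebo contrasts are tested at each location across the brain under the Section 9.1 rule, at least one false significant region per seed is nearly certain when NR has no effect: over 99% from m=90 upward, and between 91.3% and 100% in the smoothed simulations, with about 5% of locations falsely positive. The presence of significant regions in about 12 completers would then not by itself be evidence of an NR effect. The conclusion rests on the map-wise reading and on an assumed m. With only about ten pre-specified connections the figure would be about 40%.

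Two stronger readings go too far. One is that a positive map would look the same whether or not NR works: a real effect would raise both the share of locations crossing the threshold and the size of the differences. The other is that objective 2 cannot be answered at all: the objective is to measure effects, and Section 9.1 allows for 95% confidence intervals.

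The problem is confined to an optional exploratory sub-study. The RBANS primary outcome is not affected. The correction should be made, but it does not bear on the trial's main result.

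**What to change.** In Section 9.1:
- Exempt voxel- or vertex-wise imaging maps from the no-correction sentence.
- State the NR–placebo contrast and list the seeds.
- Control error across each map and across all seeds together, by cluster-wise family-wise error or false discovery rate at 5%.
- Report any uncorrected map descriptively, without the word significant.

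Optionally, pre-specify a network-level connectivity summary, chosen by the investigators, with an estimate and 95% confidence interval. This would give objective 2 an answer that does not depend on a map threshold.

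The change is a few lines of text and needs no new data, visits or participants. The downside is that fewer regions will be declared, possibly none. With 12 completers, an uncorrected two-sided paired t-test at one location has power of only 35% for an assumed standardised difference of 0.5 and 71% for 0.8, and map-level control lowers this further.
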